### **6.3 Check-In Procedures**

Subjects will check into the clinic on Day -2.

At check-in, all subjects will be evaluated to confirm they continue to meet all the inclusion criteria (Section 5.1) and none of the exclusion criteria (Section 5.2). Subjects will undergo the following assessments during the confinement period prior to dosing:

- Physical and neurological examinations
- Vital signs (temperature, respirations, blood pressure, pulse, and pulse oximetry)
- Triplicate 12-lead ECG
- Urine drug, alcohol, and cotinine screens – results must be negative for the subject to continue study participation
- Serum pregnancy test (all female subjects) – results must be negative for the subject to continue study participation
- Concomitant medication review
- AE review

### **6.4 Confinement**

Subjects will be admitted to the research center on Day -2.

Subjects in the food-effect cohorts will remain confined until after completion of the Day 20 procedures and will return for follow-up outpatient visits on Days 21-26.

Subjects will receive a follow up phone call on Day 33 (+1 day).

Subjects in the non-food-effect cohort will remain confined until after completion of the Day 17 procedures and will return for follow-up outpatient visits on Days 18-23.

Subjects will receive a follow up phone call on Day 30 (+1 day).

### **6.5 Fasting/Meals/Beverages**

#### **6.5.1 Fasting/Meals**

An optional meal may be served the evening of check-in.

All subjects in the food-effect cohorts will be required to fast for at least 10 hours before the first dose on Day 1. The subjects will fast for 4 hours thereafter.

For Days 4-17 in the food-effect cohorts and Days 1-14 for the non-food-effect cohort, all subjects will then be required to fast for at least 10 hours before consuming a required FDA standard high-fat, high-calorie breakfast. Subjects will receive the required FDA standard high-fat, high-calorie breakfast to begin 30 minutes before

scheduled administration of the dose and to end (last bite taken) within 5 minutes before dosing. The subjects will fast for 4 hours thereafter. An FDA standard high-fat (approximately 50% of total caloric content of the meal), high-calorie (approximately 1000 calories) breakfast consists of:

2 eggs fried in butter  
2 strips of bacon  
2 slices of toast with butter  
4 ounces of hash brown potatoes  
8 ounces of whole milk

This meal contains approximately 150 protein calories, 250 carbohydrate calories, and 500-600 fat calories. An equivalent meal may be substituted with documentation of the menu and caloric contents.

Standard meals will be provided at approximately 4 and 10 hours after drug administration and at appropriate times thereafter.

#### 6.5.2 Beverages

Except for 200 mL of the room temperature water provided with the study treatment, no water may be consumed for 1 hour prior to each dose through 1 hour after each dose.

At other times, subjects will be encouraged to drink water ad libitum.

### 6.6 Drug Administration

#### 6.6.1 Administration of TBI-223 Sustained Release and Immediate Release Tablets or Placebo Tablets for TBI-223

Each subject will receive the oral dose of the assigned study treatment with approximately 200 mL of room temperature water. Subjects must swallow the study medication intact. The medication should NOT be crushed or chewed. A hand and mouth check will be performed immediately after dose to ensure that the medication has been appropriately swallowed.

The subjects will remain seated, except as otherwise required for study procedures or personal needs, for the first 4 hours after dosing. Should the need to move about occur during the first 4 hours after each dose, subjects may be escorted to such procedures or activities by research personnel as deemed medically necessary. Subjects will not be allowed to lie down, except as directed by clinical staff secondary to AEs, for the first 4 hours after dosing.

#### 6.7 Blood Sampling, Processing and Shipment

Blood samples will be collected as detailed in [Appendix 1](#).

Refer to the Schedule of Events for specific blood collection time points. The Principal Investigator, in conjunction with the Sponsor, may collect additional blood if necessary for repeat laboratory or safety evaluations including AE follow-up.

After Day -1, blood for clinical labs and coagulation testing should be collected 6-7 hours postdose.

For the food-effect cohorts, a total of 60 mL (15 x 4 mL samples) will be collected from each subject for plasma predose trough pharmacokinetic analysis. A total of 204 mL (51 x 4 mL samples) will be collected from each subject for plasma postdose pharmacokinetic analysis. Approximately 144.2 mL of blood will be collected for the clinical laboratory evaluations. The total volume of blood collected from each subject will not exceed approximately 408.2 mL.

**Table 6 Total Volume of Blood to be Collected for Testing, Food-Effect Cohorts**

Reason for Collection	Number of Samples	Volume per Sample (mL)	Total Volume (mL)
Clinical labs at screening	1	12.5	12.5
Clinical labs during study (Days -1, 1, 2, 3, 4, 5, 6, 10, 14, 17, 20 and 26/end-of-study)	12	8.5	102
Coagulation (screening and Days -1, 1, 3, 4, 6, 10, 14, 17, 20, and 26)	11	2.7	29.7
Pharmacokinetic analysis (predose, trough)	15	4.0	60.0
Pharmacokinetic analysis (postdose)	51	4.0	204.0
		Total	408.2

For the non-food-effect cohort, a total of 56 mL (14 x 4 mL samples) will be collected from each subject for plasma predose trough pharmacokinetic analysis. A total of 208 mL (52 x 4 mL samples) will be collected from each subject for plasma postdose pharmacokinetic analysis. Approximately 90.9 mL of blood will be collected for the clinical laboratory evaluations. The total volume of blood collected from each subject will not exceed approximately 274.9 mL.

**Table 7 Total Volume of Blood to be Collected for Testing, Non-Food-Effect Cohort**

Reason for Collection	Number of Samples	Volume per Sample (mL)	Total Volume (mL)
Clinical labs at screening	1	12.5	12.5
Clinical labs during study (Days -1, 1, 3, 6, 10, 14, and 23/end-of-study)	7	8.5	59.5
Coagulation (screening and Days -1, 1, 6, 10, 14, and 23)	7	2.7	18.9
Pharmacokinetic analysis (predose, trough)	14	4.0	56.0
Pharmacokinetic analysis (postdose)	32	4.0	128
		Total	274.9

The Principal Investigator, in conjunction with the Sponsor, may collect additional blood if necessary for repeat laboratory or safety evaluations including AE follow-up.

#### 6.7.1 Pharmacokinetic Sampling Time Windows

Blood samples collected within the time windows listed below will not be considered deviations. Note: The 24-hour sample of Day 1 must be collected prior to the Day 2 dose.

**Table 8 Acceptable Pharmacokinetic Sampling Time Windows, Food-Effect Cohorts**

Investigation and examination	Allowable Time Window		
	Postdose		
	$\leq 24$ hours	$>24$ hours to $\leq$ Day 20	$>$ Day 20
Plasma sample collection for pharmacokinetic assessment	$\pm$ 2 minutes a	$\pm$ 5 minutes	$\pm$ 10 minutes

a: The 24-hour sample of Day 1 must be collected prior to the Day 2 dose; the 2-minute window does not apply.

**Table 9 Acceptable Pharmacokinetic Sampling Time Windows, Non-Food-Effect Cohort**

Investigation and examination	Allowable Time Window		
	Postdose		
	≤24 hours	>24 hours to ≤Day 17	>Day 17
Plasma sample collection for pharmacokinetic assessment	± 2 minutes a	± 5 minutes	± 10 minutes

a: The 24-hour sample of Day 1 must be collected prior to the Day 2 dose; the 2-minute window does not apply.

## 6.8 End-of-Study Procedures

On the day of study discharge (Day 23 for non-food-effect cohort and Day 26 for the food-effect cohorts), the following procedures will be conducted:

- Physical and neurological examinations
- Vital signs measurements (blood pressure, pulse, temperature, respirations, and pulse oximetry)
- Clinical laboratory tests (hematology, chemistry, urinalysis)
- Coagulation
- Triplicate 12-lead ECG
- Concomitant medication review
- AE assessment

Subjects will receive a follow up phone call on Day 30 (non-food-effect cohort) or Day 33 (food-effect cohorts) (+1 day).

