### 1.3 Preclinical Studies and Toxicity Studies

To support IND filing, a nonclinical development plan has been executed based upon the ICH M3(R2) guidance document, “Nonclinical Safety Studies for the Conduct of Human Clinical Trials and Marketing Authorization for Pharmaceuticals,” January 2010.

A series of in vitro and in vivo studies to evaluate the efficacy of TBI-223 were carried out. TBI-223 was evaluated against a large, diverse panel of *Mtb* clinical isolates, consisting of 96 isolates representative of all identified genetic groups of *Mtb*, broad geography and diverse drug-susceptibility profiles. The panel included MDR-TB and XDR-TB strains. The MIC of TBI-223 was found to be 1.28  $\mu$ g/mL for 90% of the strains tested with a range of 0.04 to 5. Like linezolid, TBI-223 demonstrated a mild bactericidal activity against acute mouse infections of TB as a single agent, good activity against chronic mouse infections, including additive activity within the Nix-like drug combination of bedaquiline, an ATP synthase inhibitor, and pretomanid, a nitroimidazole. This combination efficacy demonstrated a strong potential for TBI-223 to replace linezolid in the Nix trial regimen and deliver a universal treatment shortening regimen that is not confined to the XDR-TB population.

A comprehensive battery of in vitro and in vivo safety pharmacology assessments was conducted to characterize the effects of TBI-223 on the function of the nervous, respiratory, and cardiovascular systems. The battery included non-GLP studies of several cardiac ion channels with TBI-223, a GLP human Ether-à-go-go-Related Gene (hERG) assay with TBI-223, a standalone GLP single-dose cardiovascular study. Nervous system and respiratory assessments were conducted in rats administered as single doses of TBI-223.

The pharmacokinetics and oral bioavailability of TBI-223 were evaluated in mice, rats, dogs and monkeys given single or repeated daily doses of TBI-223.

In support of planned human studies, the following toxicology studies have been completed with TBI-223:

- Non-GLP, 4-week, repeat-dose, oral toxicity study in mice.
- Non-GLP, 2- and 4-week, repeat-dose, oral toxicity studies in rats.
- GLP-compliant, 4-week, repeat-dose, oral toxicity study with recovery in rats.
- Non-GLP, 5-day and 2-week, repeat-dose, oral toxicity studies in beagle dogs.
- GLP-compliant, 4-week, repeat-dose, oral toxicity study with recovery in beagle dogs.

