## 5 SUBJECT SELECTION

### 5.1 Inclusion Criteria

All volunteers must satisfy the following criteria to be considered for study participation:

1. Understands study procedures and voluntarily provides written informed consent prior to the start of any study-specific procedures.
2. Is a healthy adult male or a healthy adult female of non-childbearing potential, 19 to 50 years of age (inclusive) at the time of screening.
3. Has a body mass index (BMI)  $\geq 18.5$  and  $\leq 32.0$  ( $\text{kg}/\text{m}^2$ ) and a body weight of no less than 50.0 kg at the time of screening and check-in.
4. Is medically healthy with no clinically significant screening results, as determined by the Principal Investigator (e.g., laboratory profiles are normal up to and including Grade 1 per DMID toxicity tables; Appendix 3), medical history, vital signs, ECG, or physical/neurological examination findings. Note: If exclusionary lab criteria are met, values may be confirmed by repeat evaluation.
5. Has not used tobacco- or nicotine-containing products (including smoking cessation products), for a minimum of 6 months before dosing.
6. Females of non-childbearing potential, based on having undergone one of the following sterilization procedures at least 6 months before dosing:
  - Hysteroscopic sterilization.
  - Bilateral tubal ligation or bilateral salpingectomy;
  - Hysterectomy; or

- Bilateral oophorectomy.
- Or is postmenopausal with amenorrhea for at least 1 year before the first dose with serum FSH levels consistent with postmenopausal status (i.e., greater than 40 mIU/mL) at screening.

Or, if female of childbearing potential, must agree to use an allowable form of birth control from screening until 14 days after study completion. The following are allowed birth control methods for this study:

- Vasectomized partner (at least 6 months before dosing);
- Non-surgical permanent sterilization (e.g., Essure® procedure) at least 3 months before dosing.
- Double barrier method (e.g., diaphragm with spermicide; condoms with spermicide).
- Intrauterine device (IUD).
- Abstinence (and must agree to use a double barrier method if they become sexually active during the study);
- Implanted or intrauterine hormonal contraceptives in use for at least 6 consecutive months before study dosing; and/or
- Oral, patch, or injected contraceptives, or vaginal hormonal device (i.e. NuvaRing®), in use for at least 3 consecutive months before study dosing.

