## **7.9 Pregnancy**

The Investigator will immediately notify the Sponsor of any pregnancy that is discovered during the clinical trial. Pregnancy forms will be completed for all pregnancies reported during the study or in the 30 days after completion of the IMP. In addition, the Investigator will report to the Sponsor follow up information regarding the outcome of the pregnancy, including perinatal and neonatal outcome. Infants should be followed for 6 months.

If pregnancy is suspected while the subject is receiving IMP, the IMP will be withheld immediately until the result of the pregnancy test is known. If pregnancy is confirmed, the IMP will be permanently discontinued in an appropriate manner and the subject withdrawn from the trial. Protocol-required procedures for trial discontinuation and follow up will be performed unless contraindicated by the pregnancy.

If the Investigator becomes aware the female partner of a male subject becomes pregnant during the study or in the 30 days after the completion of IMP, consent will be requested from the female partner for collection of information on her pregnancy history and for information on the current pregnancy and birth.

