## 13 EVENTS SCHEDULE

**Table 12 Schedule of Assessments (Cohorts 1 and 2)**

	SCREEN	CHECK-IN a	Fasted dosing Day 1 and washout Day 2-3			TREATMENT (14 Days) Day 18-19 Follow-up					CHECK OUT	FOLLOW-UP			EARLY WITHDRAWAL	
			-1	1	2	3	4	5-10	11	12-17		20	21-25	26	33 (+1)	
DAY	-28 to -2	-2														
EVENT																
Informed consent and medical history	X															
Check-in questions		X														
Height, weight	X															
HIV/ hepatitis B, C	X															
Serum pregnancy test b	X	X														
FSH b	X															
Urine drug/alcohol/cotinine screen	X	X														
Safety Labs (hematology, chemistry) c	X		X	X	X	X	X	X c		X c		X		X	X	
Coagulation d	X		X	X		X	X	X d		X d		X		X	X	
Urinalysis e	X		X	X		X	X	X e		X e		X		X		
Physical and neurological exams f	X	X	X	X	X	X	X	X f		X f			X		X	
Vital signs (blood pressure, pulse, temperature, respiration rate, and pulse oximetry) g	X	X		X	X	X	X	X	X	X	X	X	X		X	
Concomitant medication review h			←							→						
Adverse events i			←							→						

Protocol TBI-223 CL-002 Version 1.0

	SCREEN	CHECK-IN a	Fasted dosing Day 1 and washout Day 2-3				TREATMENT (14 Days) Day 18-19 Follow-up				CHECK OUT	FOLLOW-UP			EARLY WITHDRAWAL
			-1	1	2	3	4	5-10	11	12-17		20	21-25	26	33 (+1)
DAY	-28 to -2	-2													
EVENT															
Dose j				X			X	X	X	X					
12-lead safety ECGs k	X	X	X	X			X	X		X	X		X		X
Plasma for predose trough PK l,m				X			X	X	X	X					
Plasma for Postdose PK n				X	X	X	X			X	X	X			

ECG = electrocardiogram; FSH = follicle-stimulating hormone; HIV = human immunodeficiency virus; PK = pharmacokinetic.

- a. Confinement to start at Check-in (evening of Day -2) and continue until 72 hours after dosing on Day 17.
- b. Serum pregnancy test at screening and at check-in for females only. FSH completed for postmenopausal females only.
- c. Blood will be collected for safety labs (hematology and chemistry) at Screening and Day -1 and at 6-7 hours postdose on Days 1, 2, 3, 4, 6, 10, 14, 17, and on Days 20 and 26
- d. Blood for coagulation testing will be collected at Screening and Day -1, and 6-7 hours postdose on Days 1, 3, 4, 6, 10, 14, 17, and on Days 20 and 26.

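### No pregnancy test is scheduled after check-in on Day -2, so an early pregnancy exposed to study drug may go unrecognised; a test at discharge is a cheap improvement

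*Protocol*

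**What the plan says.** **Timing of tests.** Footnote b of Table 12 reads "Serum pregnancy test at screening and at check-in for females only", and Table 13 carries the same footnote for Cohort 3. Section 6.3 states "Subjects will check into the clinic on Day -2" and makes the result a condition of going on: "Serum pregnancy test (all female subjects) – results must be negative for the subject to continue study participation". Neither table marks a pregnancy test in any dosing, check-out, follow-up or early-withdrawal column. Section 6.9.2 names a pregnancy test among the laboratory evaluations but leaves its timing to the schedule.

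**Discharge.** Section 6.8 begins "On the day of study discharge (Day 23 for non-food-effect cohort and Day 26 for the food-effect cohorts), the following procedures will be conducted". Its laboratory items are "Clinical laboratory tests (hematology, chemistry, urinalysis") and coagulation, alongside examinations, vital signs and ECG. Pregnancy is not on the list. Section 8.4 sends subjects who stop early through the same list.

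**Who may enrol.** Criterion 2 of Section 5.1 limits women to those of non-childbearing potential. Criterion 6 then provides that "if female of childbearing potential, must agree to use an allowable form of birth control from screening until 14 days after study completion".

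**What happens if a pregnancy occurs.** Section 7.9 requires the sponsor to be told at once of a pregnancy discovered in the trial, and adds "Pregnancy forms will be completed for all pregnancies reported during the study or in the 30 days after completion of the IMP". It also asks for follow-up of the outcome and of the infant. Where pregnancy is suspected during dosing, it withholds study drug until a test result is known.

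**The concern.** The protocol treats fetal exposure as a risk to be managed. It excludes pregnant women, demands a negative test at check-in, sets contraception rules for both sexes, and follows infants for 6 months. Yet every scheduled test comes before the first dose. After that, the reporting duty in Section 7.9 depends on someone suspecting or reporting a pregnancy.

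Section 1.3 introduces its list with "the following toxicology studies have been completed with TBI-223" and names repeat-dose and genetic toxicology studies, but no reproductive study. The protocol therefore gives no basis for treating an unrecognised exposure as unimportant. At stake is a pregnancy exposed to a full course of study drug that leaves the trial unrecognised, absent from both the safety data and the outcome follow-up.

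**Working it through.** The plan gives no figure to reproduce here. The check is a reading of the schedules and a count of days.

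**Inputs.**
- Last scheduled test: Day -2 (Section 6.3; footnote b of Tables 12 and 13).
- First dose: Day 1. Last dose: Day 17 in Cohorts 1 and 2, Day 14 in Cohort 3 (synopsis).
- Discharge visit: Day 26 or Day 23. Telephone call: Day 33 or Day 30, each +1 day (Section 6.8).
- End of confinement: Day 20 or Day 17 (Section 6.4).
- Assumption: there is no Day 0, so Day -2 to Day *d* is *d* + 1 days.
- Assumption: the 30-day window in Section 7.9 starts at the last dose.

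| | Cohorts 1 and 2 | Cohort 3 |
|---|---|---|
| Last test to first dose | 1 + 1 = 2 days | 1 + 1 = 2 days |
| Last test to last dose | 17 + 1 = 18 days | 14 + 1 = 15 days |
| Last test to discharge visit | 26 + 1 = 27 days | 23 + 1 = 24 days |
| Last test to telephone call | 33 + 1 = 34 days | 30 + 1 = 31 days |
| Doses after the last test | 1 + 14 = 15 | 14 |
| Scheduled pregnancy tests after first dose | 0 | 0 |
| Last dose to discharge visit | 26 − 17 = 9 days | 23 − 14 = 9 days |
| End of confinement to discharge visit | 26 − 20 = 6 days | 23 − 17 = 6 days |
| End of 7.9 window | 17 + 30 = Day 47 | 14 + 30 = Day 44 |
| Window left after the call | 47 − 33 = 14 days (13 if Day 34) | 44 − 30 = 14 days (13 if Day 31) |

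**Which pregnancies matter.** There are three cases:
1. *Conception shortly before Day -2.* The check-in test may be negative and all doses may follow. By discharge the pregnancy is 27 or 24 days older than at the last test. The documents give no detection limit for the assay, so I assume that a very recent conception can be missed on Day -2 and would show by discharge.
2. *Conception during dosing.* Subjects are confined until after the last dose, so this is unlikely.
3. *Conception around or after release.* The discharge visit is only 6 days after release, so a test there would probably miss it.

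A discharge test therefore addresses the first case.

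**Number at risk.** The protocol does not say how many women of childbearing potential will enrol. Three cohorts with 9 subjects each on active drug give 3 × 9 = 27, so the exposed number lies between 0 and 27. It is 0 if criterion 2 governs.

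**The case against.** A reader might infer that the schedule contradicts Section 7.9. It does not. That section covers pregnancies that are discovered or reported; it sets a reporting duty and promises no surveillance.

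Nor is self-report the only route to detection. Section 7.9 provides a test on suspicion during dosing, Section 6.7 allows extra blood for safety evaluations, adverse-event questions are asked daily, and there is a discharge examination and a later call. These routes exist, but each depends on a suspicion or a report, and the test in Section 7.9 is tied to the dosing period.

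A reader might also give conception during dosing the same weight as conception before check-in. Confinement makes the former remote. The contraception required from screening also makes the latter uncommon, and the permitted methods include intrauterine devices and hormonal methods as well as barriers and abstinence.

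The benefit is limited too. The discharge visit falls 9 days after the last dose, so a test then prevents no exposure in completers, and it leaves the later part of the 30-day window untested. If criterion 2 governs, no one is at risk. The absence of a reproductive study from Section 1.3 is an inference from a list; details are left to the Investigator's Brochure, which is not at hand.

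All of this stands and reduces the point to a modest one. It does not remove the case of an early pregnancy missed on Day -2.

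**Conclusion.** The point holds as a cheap improvement. No pregnancy test is scheduled after Day -2 in any cohort, and the discharge and early-termination list has none, while criterion 6 admits women of childbearing potential and Section 7.9 expects pregnancies to be reported and followed. This is a gap between a duty and the means of detection.

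Its size is one narrow scenario: a conception too early to detect at check-in, up to 15 or 14 doses, and a discharge visit 27 or 24 days after the last test. The conclusion rests on criterion 6 being applied as written and on the assumption about detection stated above. The documents support no estimate of how often this would occur.

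**What to change.** First reconcile inclusion criteria 2 and 6 in Section 5.1, which disagree on whether women of childbearing potential may enrol.

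If they remain eligible, add a serum pregnancy test for them to the Section 6.8 list. Mark it in Table 12 at Day 26, in Table 13 at Day 23, and in the early-withdrawal column of both. Blood for clinical laboratory tests is already drawn at those visits. If they are not eligible, no added test is needed on this ground, and the contraception wording in criterion 6 should be aligned.

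The cost is one extra assay per woman of childbearing potential, with no added visit. Testing all female subjects would be broader than this concern requires. The test supports detection and follow-up only: it will not prevent exposure in completers, and it will not find conceptions around or after release from confinement.
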